### **3.7.3. Selection of Non-Efficacy Data in the Event of Multiple Records in an Analysis Visit Window**

Depending on the statistical analysis method, single values may be required for each analysis window. For example, change from baseline by visit usually requires a single value, whereas a time-to-event analysis would not require 1 value per analysis window.

If multiple valid, nonmissing, continuous measurements exist in an analysis window, records will be chosen based on the following rules if a single value is needed:

- In general, the baseline value will be the last nonmissing value on or prior to the first dose date of study drug, unless otherwise specified. If multiple measurements occur on the same day, the last nonmissing value prior to the time of first dose of study drug will be considered as the baseline value. If these multiple measurements occur at the same time or the time is not available, the average of these measurements (for continuous data) will be considered the baseline value.
- For postbaseline visits:
  - The record closest to the nominal day for that visit will be selected.
  - If there are 2 records that are equidistant from the nominal day, the later record will be selected.
  - If there is more than 1 record on the selected day, the average will be taken, unless otherwise specified.

If multiple valid, nonmissing, categorical measurements exist in an analysis window, records will be chosen based on the following rules if a single value is needed:

- For baseline, the last available record on or prior to the date of the first dose of study drug will be selected. If there are multiple records with the same time or no time recorded on the same day, the value with the lowest severity will be selected (eg, normal will be selected over abnormal for safety ECG findings).
- For postbaseline visits:
  - The record closest to the nominal day for that visit will be selected.
  - If there are 2 records that are equidistant from the nominal day, the later record will be selected.
  - If there is more than 1 record on the selected day, the value with the worst severity will be taken (eg, abnormal will be selected over normal for safety ECG findings), unless otherwise specified.

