#### **3.7.2. Analysis Visit Windows**

Subject visits may occur on days not specified in the protocol (eg, unscheduled visits). Therefore, for the purpose of analysis, observations will be assigned to analysis windows.

In general, the baseline value will be the last nonmissing value on or prior to the first dose date of study drug.

**Table 3-1 Analysis Visit Windows for Joint Count Assessment, HAQ-DI, PhGA, PtGA, and On-Treatment CRP, Safety Laboratory Data, Weight, Vital Signs, ECG**

Nominal Visit	Nominal Study Day	Lower Limit	Upper Limit
Baseline	1	(none)	1
Week 2	15	2	22
Week 4	29	23	43
Week 8	57	44	71
Week 12	85	72	≥ 85

The analysis windows for joint count assessment, health assessment questionnaire - disability index (HAQ-DI) (including the patient’s assessment of pain), physician’s global assessment of disease activity (PhGA), patient’s global assessment of disease activity (PtGA), on-treatment CRP, safety laboratory, weight, vital signs and electrocardiogram (ECG) are provided in [Table 3-1](#). CRP, safety laboratory, weight, vital signs, and ECG data collected up to the last dose date of any study drug + 3 days are considered to be on-treatment data.

CRP, safety laboratory, weight, vital signs, and ECG data collected after last dose date of any study drug + 3 days will be considered as posttreatment data and will be summarized up to last dose date plus 30 days, and labeled as “FU-Week 4”. Data obtained after last dose date plus 30 days will be excluded from the summaries, but will be included in the listings.

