## 6. EFFICACY ANALYSES

### 6.1. General Considerations

The primary analysis set for efficacy analyses will be the FAS, defined in Section 3.1.2.

If multiple valid, nonmissing efficacy measurements exist in an analysis window, records will be chosen based on the following rules if a single value is needed:

- If record collection date/time is known, latest record will be taken
- If time is unknown, the worst scenario will be selected

For the composite endpoints including DAS28(CRP), ACR 20/50/70, SDAI, and CDAI, we use the following steps unless otherwise specified:

- Step 1: Put each component value into a visit window
- Step 2: Within each visit window, select the component data point for analysis
- Step 3: Combine these selected data points within each visit window across the components.

Below are the descriptions for the imputation methods that will be used throughout the efficacy analyses:

- Observed case (OC): missing values remain missing. For the above composite endpoints, in the case that some components are missing, the composite endpoint assessment will be derived based on the non-missing components. If non-missing components are not sufficient to determine final composite endpoint, then the composite endpoint will be considered as missing.
- Last observation carried forward (LOCF): For the above composite endpoints, First LOCF all components over all visits, then combine the components as mentioned above.
- Non-responder imputation (NRI): For all binary response measurements, starting from OC, all missings will be treated as non-responders.

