### **7.2.1. Summaries of Numeric Laboratory Results**

Descriptive statistics will be provided by treatment group for each laboratory test specified in the study protocol as follows:

- Baseline values
- Values at each postbaseline visit
- Change from baseline at each postbaseline visit

A baseline laboratory value will be defined as the last measurement obtained on or prior to the date/time of first dose of any study drug. Change from baseline to a postbaseline visit will be defined as the visit value minus the baseline value. The mean, median, Q1, Q3, minimum, and maximum values will be displayed to the reported number of digits; SD values will be displayed to the reported number of digits plus 1.

Median (Q1, Q3) of the observed values for selected laboratory tests will be plotted using a line plot by treatment group and visit.

In the case of multiple values in an analysis window, data will be selected for analysis as described in Section 3.7.3.

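### SAP 3.7.3 cuts the baseline for categorical safety data at the date, not the time, of first dose, so the ECG assessment and QTcF can take different baselines from the same Day 1 recordings

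*SAP*

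**What the plan says.** The SAP states the baseline cut-off in several places, and not always in the same way.

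- **General rule (3.7.2), by date:** "In general, the baseline value will be the last nonmissing value on or prior to the first dose date of study drug". Table 3-1 gives Baseline no lower limit and an upper limit of Day 1, with no division at the dose. The Week 2 window opens on Day 2.
- **Continuous non-efficacy data (3.7.3), by time when a day has several records:** the section repeats the date rule, then adds "If multiple measurements occur on the same day, the last nonmissing value prior to the time of first dose of study drug will be considered".
- **Categorical non-efficacy data (3.7.3), by date:** "For baseline, the last available record on or prior to the date of the first dose of study drug will be selected". No time condition follows. There is only a tie rule, under which the least severe value is taken: "If there are multiple records with the same time or no time recorded on the same day, the value with the lowest severity will be".
- **Numeric laboratory values (7.2.1), by date and time:** "A baseline laboratory value will be defined as the last measurement obtained on or prior to the date/time of first dose of any study drug". Section 7.3 uses an equivalent cut-off for weight and vital signs.
- **ECG (7.5.1 to 7.5.3):** no baseline definition. The investigator's assessment is categorical and goes into a shift table. QT and QTcF are continuous and are summarized as values and changes from baseline.
- **Efficacy (6.1):** for several records in a window, "If record collection date/time is known, latest record will be taken", with no exception for the Baseline window.

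**The concern.** A baseline should describe the subject before exposure. The continuous rule in 3.7.3 provides for a Day 1 with records on both sides of the dose and resolves it correctly. The categorical rule in the same section does not. It takes the last record of the day, even if that record was made after dosing.

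ECG is where this shows, because one recording yields both a categorical result and continuous intervals, and no ECG-specific definition overrides 3.7.3. At stake is the meaning of the baseline rows of the ECG shift table, and whether sections 7.5.1 and 7.5.2 describe change from the same reference.

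**Working it through.** The SAP gives no figure on this point, so the check is to apply its rules to a constructed subject. Assume a first dose at 10:00 on Day 1.

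**Case A: two timed Day 1 ECGs, 08:00 normal and 12:00 abnormal.**

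| Rule | Cut-off | Record taken as baseline |
|---|---|---|
| 3.7.3 continuous (QTcF) | time of first dose | 08:00, pre-dose |
| 3.7.3 categorical (investigator's assessment) | date of first dose | 12:00, post-dose |

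Because Baseline runs to the end of Day 1 and Week 2 starts on Day 2, the 12:00 reading belongs to no post-baseline visit column. If the Week 2 ECG is abnormal, the shift table shows abnormal to abnormal. Measured from the 08:00 reading, it would show normal to abnormal. A shift has been masked.

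**Case B: the same times, 08:00 abnormal and 12:00 normal.** The categorical rule takes the normal 12:00 reading. An abnormal Week 2 ECG then shows as normal to abnormal, although the subject was abnormal before dosing. A shift has been created. The direction of the error is therefore not fixed.

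**Case C: the two Day 1 readings have no recorded time.** The tie rule takes the lower severity, so the normal reading is the baseline. The error of Case A does not arise.

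**Case D: one screening ECG and a single post-dose ECG on Day 1.** The time condition for continuous data is written only for several records on the same day. Read literally, the date rule takes the post-dose record for QTcF as well as for the investigator's assessment. The two agree, but on a post-dose baseline. Laboratory values, weight and vital signs avoid this through 7.2.1 and 7.3.

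**Where treatment-emergence is defined.** Adverse events count by onset date, Day 1 included, with no comparison with a baseline record (7.1.5.1). Graded laboratory abnormalities are compared with baseline (7.2.2.1), and 7.2.1 sets that baseline by date and time. Neither uses the categorical rule of 3.7.3.

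**Scale.** Section 1.2 plans 20 subjects per group. One subject placed in a different cell moves the two cells concerned by 1/20 = 5 percentage points each, if all 20 have non-missing ECG results at baseline and at that visit (7.5.1 removes subjects with missing values from the denominator). The number of such subjects cannot be derived from the SAP.

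**Efficacy.** Applied to the Baseline window, the rule in 6.1 would also take a later Day 1 record over an earlier one, whichever side of the dose it fell on. The gap is the same by wording. Nothing in the SAP shows that joint counts, HAQ-DI or global assessments are repeated after dosing on Day 1.

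**The case against.** The strongest reply is that this may never occur. It needs a post-dose Day 1 record, with its time, later than the pre-dose one. The Day 1 schedule is not in the SAP and may properly sit in the protocol. The table concerned is descriptive, no formal testing is planned for it, every ECG assessment still appears in the by-subject listing, and the rule is the same in all four groups. All of this stands, and it limits the point to a minor one.

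Three stronger readings are tempting, and the document does not support them.

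- A reader might infer that a Day 1 post-dose finding can no longer count as treatment-emergent. The SAP defines that term only for adverse events and laboratory abnormalities, and neither depends on the categorical baseline rule. A Day 1 ECG finding reported as an adverse event is still treatment-emergent.
- A reader might take the 5 points as a fall in an emergent ECG rate. The SAP produces no such rate. The figure describes only cells of a shift table.
- A reader might conclude that ECG abnormality is understated in the active groups. That assumes an acute drug effect on the ECG which the SAP does not state, and Case B shows that the error can run the other way.

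What the reply does not remove is the conflict itself. The continuous rule in 3.7.3 expressly provides for records on both sides of the dose, and in that situation the categorical rule gives the wrong baseline. This is a stated rule, not an omission left to the protocol.

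**Conclusion.** The point holds as an inconsistency of definition with a limited consequence. For a subject with timed ECGs before and after dosing on Day 1, the SAP gives the investigator's assessment a post-dose baseline and QTcF a pre-dose one, and a shift can be masked or created in a descriptive table.

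The size is unknown and is zero if no timed post-dose Day 1 record exists. The conclusion rests on a literal reading of 3.7.3 and on the absence of an ECG baseline definition in 7.5. The efficacy gap in 6.1 is one of wording only and is no ground for doubting the primary analysis. Sample size, power and significance level are untouched.

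**What to change.** Use one cut-off throughout: at or before the date/time of first dose of any study drug, as 7.2.1 and 7.3 already have it.

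- In the categorical baseline rule of 3.7.3, replace the date cut-off with this one.
- Make the same change in the general rule of 3.7.2 and where 3.7.3 repeats it for continuous data, which also settles Case D.
- In 6.1, state that the baseline record is chosen under this cut-off before the rule for the latest record is applied.
- Keep the existing tie rules for records without a time.

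The cost is a few wording edits and a minor change to the baseline derivation. No new data are needed.

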## 4. SUBJECT DISPOSITION

### 4.1. Subject Enrollment and Disposition

A summary of subject enrollment will be provided by treatment group for each country within each geographic region and investigator within a country. The summary will present the number and percentage of subjects enrolled. For each column, the denominator for the percentage calculation will be the total number of subjects analyzed for that column.

A similar enrollment table will be provided by stratification factor stratum. The denominator for the percentage of subjects in the stratum will be the total number of enrolled subjects. If there are discrepancies in the value used for stratification assignment between the IXRS and the clinical database, the value collected in the clinical database will be used for the summary. A listing of subjects with discrepancies in the value used for stratification assignment between the IXRS and the clinical database at the time of data finalization will be provided.

The randomization schedule used for the study will be provided as an appendix to the CSR.

A summary of subject disposition will be provided by treatment group. This summary will present the number of subjects screened, the number of subjects not randomized, the number of subjects who met all eligibility criteria but were not randomized with reasons subjects were not randomized, the number of subjects randomized, and the number of subjects in each of the categories listed below:

- Safety Analysis Set
- Full Analysis Set
- PK Analysis Set
- PK Substudy Analysis Set
- Completed study drug
- Did not complete study drug with reasons for premature discontinuation of study drug
- Continuing study (if applicable)
- Completed study
- Did not complete study with reasons for premature discontinuation from the study

For the status of study drug and study completion and reasons for premature discontinuation, the number and percentage of subjects in each category will be provided. The denominator for the percentage calculation will be the total number of subjects in the Safety Analysis Set corresponding to that column. In addition, a flowchart will be provided to depict the subject disposition.

The following by-subject listings will be provided by treatment group and subject ID number (in ascending order) to support the above summary tables:

- Reasons for premature study drug or study discontinuation
- Reasons for screen failure (will be provided by screening ID number in ascending order)
- Lot number and kit ID of assigned study drugs

#### **4.2. Extent of Study Drug Exposure and Adherence**

Extent of exposure to study drug will be examined by assessing the total duration of exposure to study drug and the level of adherence to the study drug specified in the protocol.

##### **4.2.1. Duration of Exposure to Study Drug**

Total duration of exposure to any study drug will be defined as (last dose date of any study drug - first dose date of any study drug + 1), regardless of any temporary interruptions in study drug administration and will be expressed in weeks using up to 1 decimal place (eg, 4.5 weeks).

If the last study drug dosing date is missing, the latest date among the study drug end date, clinical visit date, laboratory sample collection date, weight and vital signs assessment date that occurred during the on-treatment period will be used.

The total duration of exposure to any study drug will be summarized using descriptive statistics and using the number (ie, cumulative counts) and percentage of subjects exposed through the following time periods: Baseline (Day 1), Week 2 (Day 15), Week 4 (Day 29), Week 8 (Day 57), and Week 12 (Day 85).

Summaries will be provided by treatment group for the Safety Analysis Set. No formal statistical testing is planned.

##### **4.2.2. Adherence to Study Drug**

Adherence will be calculated separately for GS-9876/PTM (tablets) and filgotinib/PTM (tablets).

The total number of tablets administered will be summarized using descriptive statistics.

The presumed total number of tablets administered to a subject will be determined by the data collected on the drug accountability CRF using the following formula:

$$\begin{aligned} \text{Total Number of Tablets Administered} = \\ (\Sigma \text{No. of Tablets Dispensed}) - (\Sigma \text{No. of Tablets Returned}) \end{aligned}$$

If a bottle is dispensed and the bottle is returned empty, then the number of tablets returned will be entered as zero. If a bottle is dispensed but not returned (missing), the number of tablets administered will be counted as zero.

#### 4.2.2.1. On-Treatment Adherence

The level of on-treatment adherence to the study drug will be determined by the total amount of study drug administered relative to the total amount of study drug expected to be administered during a subject's actual on-treatment period based on the study drug regimen.

The level of on-treatment adherence will be expressed as a percentage using the following formula:

$$\text{On-Treatment Adherence (\%)} = \left( \frac{\text{Total Amount of Study Drug Administered}}{\text{Study Drug Expected to be Administered on Treatment}} \right) \times 100$$

Note: If calculated adherence is greater than 100%, the result will be set to 100%.

Study drug expected to be administered for GS-9876/PTM (tablets) = 1 tablet  $\times$  total duration of exposure to any study drug (days).

Study drug expected to be administered for filgotinib/PTM (tablets) = 2 tablets  $\times$  total duration of exposure to any study drug (days).

Descriptive statistics for the level of on-treatment adherence with the number and percentage of subjects belonging to adherence categories (eg, < 80%,  $\geq$  80 to < 90%,  $\geq$  90%) will be provided by treatment group for the Safety Analysis Set.

Categorical displays will be presented for the number of subjects who are at least 80% adherent to their study drug regimen (ie, adherence is  $\geq$  80% for each study drug).

No formal statistical testing is planned.

A by-subject listing of study drug administration and drug accountability will be provided separately by treatment group, subject ID number (in ascending order) and visit (in chronological order).

#### 4.3. Protocol Deviations

Subjects who did not meet the eligibility criteria for study entry, but enrolled in the study will be summarized. The summary will present the number and percentage of subjects who did not meet at least 1 eligibility criterion and the number of subjects who did not meet specific criteria by treatment group based on the All Randomized Analysis Set. A by-subject listing will be provided for those subjects who did not meet at least 1 eligibility (inclusion or exclusion) criterion. The listing will present the eligibility criterion (or criteria if more than 1 deviation) that subjects did not meet and related comments, if collected.

Protocol deviations occurring after subjects entered the study are documented during routine monitoring. The number and percentage of subjects with important protocol deviations by deviation reason will be summarized by treatment group for the All Randomized Analysis Set. A by-subject listing will be provided for those subjects with important protocol deviation.

## 5. BASELINE CHARACTERISTICS

### 5.1. Demographics

Subject demographic variables will be summarized by treatment group and overall using descriptive statistics for continuous variables, and using number and percentage of subjects for categorical variables. The summary of demographic data will be provided for the Safety Analysis Set for the following:

- age (on the first dose date of any study drug) as a continuous variable
- sex at birth (male, female)
- race
- ethnicity (Hispanic/Latino, not Hispanic/Latino)

A by-subject demographic listing, including the informed consent date, will be provided by treatment group and subject ID number in ascending order.

### 5.2. Other Baseline Characteristics

Other baseline characteristics include:

- prior inadequate response to biologic therapy and number of prior biologics used
- geographic region
- concurrent use and weekly dose of methotrexate (refer to [Appendix 2](#) for methotrexate medication list)
- concurrent use of hydroxychloroquine (refer to [Appendix 2](#) for hydroxychloroquine medication list)
- concurrent use of corticosteroid (refer to [Appendix 3](#) for the definition of corticosteroid medications)
- height (cm)
- weight (kg)
- body mass index (BMI; in kg/m^2)
- baseline swollen joint count based on 66 joints (SJC66) and tender joint count based on 68 joints (TJC68)

- baseline swollen joint count based on 28 joints (SJC28) and tender joint count based on 28 joints (TJC28)
- baseline HAQ-DI
- baseline patient's pain assessment
- baseline DAS28(CRP)
- baseline patient's global assessment of disease activity
- baseline physician's global assessment of disease activity
- baseline Simplified Disease Activity Index (SDAI) and Clinical Disease Activity Index (CDAI)
- baseline CRP (mg/L)
- duration of RA (years)

duration of RA (years) = ((first dose date) – (date of initial diagnosis) + 1 day) / 365.25. If the date of initial diagnosis is incomplete, then the following rules will be applied:

- Missing day: use the first of the month.
- Missing month: use January.

These baseline characteristics will be summarized by treatment group and overall using descriptive statistics for continuous variables and using number and percentage of subjects for categorical variables. The summary of baseline characteristics will be provided for the Safety Analysis Set.

A by-subject listing of other baseline characteristics will be provided by treatment group and subject ID number in ascending order.

